### **3.4 Outcome Measures**

Clear nail: The specifications for clear nail are described below. The 95% one-sided confidence interval (i.e., lower bound only) around the observed response rate as described below should be  $\geq 50\%$ .

We will monitor whether subjects attain 3 mm or more of clear nail growth post-treatment. We will verify by taking a photograph prior to every treatment to assess the change in millimeters (mm) of clear nail bed. Millimeters (mm) of clear nail from the base of the toenail will be determined from digital photographs of the toenail and verified via software. The change in mm of clear nail bed will be calculated as the difference in mm of clear nail bed from baseline measurement to the measurement at the end of the procedure administration phase.

An increase in mm of clear nail between the two measurement points indicates that the toenail has improved and is positive for study success. A decrease in mm of clear nail between the two measurement points indicates that the toenail has worsened and is negative for study success.

Individual toenail success criterion is defined as 3 millimeter (mm) or more of clear nail growth as evaluated relative to baseline.

Length of the unaffected part of the target nail is measured in millimeters along the midpoint from the nail fold to the proximal border of the affected part (lowest point affected) along the midpoint of the target nail. Change from Baseline is: (Baseline value subtracted from 6-month treatment value). P-value shall be based on analysis of variance (ANOVA) with treatment and pooled center. Statistics will be provided for the adjusted least square mean.

To ensure adequate photographic quality and to maximize our ability to compare photographs across timepoints and across subjects, a standardized photography protocol will be put in place. Photographs shall be of high quality and high resolution. An internal scale (e.g. ruler) will be included in all images to allow objective measurement of millimeters of clear nail regardless of magnification of the image.

**Mycology:** Among toenails which are deemed responders based on the “clear nail” criteria, we will also assess for negative mycology (negative stain with concurrent negative culture, or two negative cultures from the same nail).

**Follow-up:** The goal of treatments for onychomycosis is elimination of the fungal organism and full clearance of the nail. Follow-up for this indication should be based on the anticipated time for complete nail regrowth, which is approximately 6 months. Longer follow-up times will be helpful for assessing recurrence rates. To control for loss of subjects who do not exhibit the desired visual outcome, subjects who drop out or are lost to follow-up will be considered as treatment failures for this indication.

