## 1.0 Protocol Summary

Title	A Pilot Study Evaluating the Feasibility and Usability of ToeFX Light Therapy Device for Mild to Moderate Distal Subungual Onychomycosis (DSO) of the Toenail
Short Title	ToeFX light therapy pilot
Methodology	Open label, prospective, multi-site, multi-investigator
Study Sites	
Hamilton Foot Clinic [name]
 
Bruyere Foot Specialists [name]
 
Wilson Foot Clinic [name]

Number of Study Subjects	100 subjects
Diagnosis and Main Inclusion Criteria	
Healthy males or females who meet the following criteria:
 
 
• are between 18-75 years of age.
 
• have a clinical diagnosis of mild to moderate DSO in the nail of at least one great toe, with 20% to 50% clinical involvement of the target toenail, without dermatophytomas or lunula (matrix) involvement, without lunular or proximal involvement.
 
• exhibit positive mycology results (ie, KOH test and culture of a dermatophyte) from the target great toenail, confirming common dermatophytes such as T. rubrum.
 
• are willing to abstain from any other treatment for onychomycosis for the duration of the pilot study.
 

Study Product and Planned Use	The ToeFX Light Therapy system is intended as a safe, effective and non-invasive treatment for nail fungus.

	This device will be used in accordance with the attached protocol. This study will be an open-label, prospective pilot study. The subjects will be 100 patients with mild to moderate onychomycosis. The purpose of the study is to establish the efficacy of the ToeFX device, which has shown compelling results in in vitro and ex vivo (cadaver) studies but has not been tested in patients.
Primary Endpoint	Technical Success: We will monitor (a) whether subjects attain 3 mm or more of clear nail growth post-treatment (b) whether subjects show mycological cure of their infection, as verified by culturing.
Secondary Endpoints	
 
• Usability and form factor reported by clinicians
 
• Satisfaction with the treatment reported by patients
 

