### Intended Users

User	Qualifications	Role & Location during ToeFX treatment	Interaction with ToeFX system
Chiropodist	
 
- Doctor of Chiropody
 
- Training in diagnosis and treatment of onychomycosis
 
	
 
- Assess severity of nail fungus and administer or supervise administration of treatment
 
	
 
- Deploys ToeFX system by administration of topical formulation
 
- Positions ToeFX light source over the infected area
 
- Removes the ToeFX light source at the treatment's end point.
 

Podiatrist	
 
- Doctor of Podiatry
 
- Training in diagnosis and treatment of onychomycosis
 
	
 
- Assess severity of nail fungus and administer or supervise administration of treatment
 
	
 
- Deploys ToeFX system by administration of topical formulation
 
- Positions ToeFX light source over the infected area
 
- Removes the ToeFX light source at the treatment's end point.
 

Physician assistant	
 
- Bachelor of Health Sciences (Physician Assistant specialization)
 
- Training supporting foot care clinicians
 
	
 
- Assist with administration of ToeFX treatment
 
- Collection of data, taking photographs of affected area
 
	
 
- May position light source over affected area and/or remove light source upon conclusion of the treatment.
 

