### 3.2 Study Design

Study Type:	Interventional (clinical trial)
Actual Enrollment:	100 participants
Masking:	None (Open Label)
Primary Purpose:	Treatment
Study Start Date:	Immediately upon approval by Health Canada

Arm	Intervention/treatment
Arm 1 Red light only	Core technology. Formulation and red light only. Apply photosensitizer; allow to penetrate for 15 minutes; apply red light for 15 minutes.
Arm 2 Red and blue light	Apply photosensitizer; place foot under blue light and allow to penetrate for 15 minutes. Apply red light for 15 minutes.

Arm 1 will test the core technology of the ToeFX system; this study reproduces protocols described in the literature (see ‘Previous Studies’ in Section 6.02). Arm 2 pairs the core technology with application of blue light. After application of the formulation, the nail is exposed to blue light at a wavelength of 450-470 nm and an intensity of 200 mW/cm^2. The blue light has no effect on the photosensitizer; however, several research groups have confirmed that exposure to mild blue light can have anti-inflammatory effects that would improve patient

outcomes (see ‘Previous Studies’ in Section 6.02). We will assess whether inclusion of blue light in the protocol affects the clinical outcome.

Debridement should be done prior to each treatment. Debridement should not be carried out more proximally than the most proximal margin of the dystrophic nail, as this can interfere with assessment of clear nail area attributable to the device intervention. Clinician should debride the nail and apply the photosensitizer formula and let it penetrate for 15 minutes, then if applicable apply the blue light (450-470 nm). Apply the red light (640 nm) for 15 minutes. The treatment is administered 12 times over the course of 1 year.

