### **3.3 Control**

Our study cohort will be compared to known values published in a large multicenter trial of the topical solution Jublia (manufactured by Valeant). Jublia is a once-daily treatment of 10% w/w efinaconazole for the treatment of onychomycosis. Jublia showed a complete cure rate of 15-18% in a study of two groups of 800 patients.

We will follow the inclusion and exclusion criteria defined in the Jublia trial. Patients in the Jublia study showed 20% to 50% clinical involvement of the area of the target great toenail, without dermatophytomas or lunula (matrix) involvement. Patients had positive dermatophyte culture and positive potassium hydroxide (KOH) examination from the target toenail and were not excluded for concomitant *Candida* infection. Patients were assessed for clear nail.

Based on previously published studies of photodynamic therapy for onychomycosis, we expect to observe a complete cure rate on the order of 50-80%. Given the large difference in the observed cure rate for Jublia and the anticipated cure rate for the ToeFX Light Therapy device, a sample size of 100 patients is adequate to establish statistical significance of our results.

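### Nothing in the plan hides arm or visit from whoever reads the nail photographs, so a reading error that differs by visit or arm would pass into the 3 mm responder rate or the arm comparison

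*Combined protocol and SAP*

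**What the plan says.** **Masking and roles.** Section 3.2 of the combined protocol and SAP gives masking as "None (Open Label"). The Intended Users table under section 2.2 has the physician assistant help give the treatment and also lists "Collection of data, taking photographs of affected area" for that role. Section 3.1 has a clinician or delegate take the photographs and prepare the table of responders.

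**Measurement.** Under section 3.4, clear nail is "determined from digital photographs of the toenail and verified via software". It is measured along the midline from the nail fold to the proximal border of the affected part. A standardised photography protocol is promised, and every image contains a ruler. The change is end of treatment minus baseline; a later paragraph of the same section refers to a 6-month value.

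**Use of the reading.** "Individual toenail success criterion is defined as 3 millimeter (mm) or more of clear nail growth as evaluated relative to baseline". The decision rule is: "The 95% one-sided confidence interval (i.e., lower bound only) around the observed response rate as described below should be" at least 50%. Mycology follows from the same reading: "Among toenails which are deemed responders based on the “clear nail” criteria, we will also assess for negative mycology". The Protocol Summary names mycological cure as the second part of the primary endpoint.

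**Comparisons.** The control in section 3.3 is a set of published values. Section 3.2 also plans to assess whether adding blue light changes the outcome.

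**The concern.** The millimetre value depends on where someone places the proximal border of the affected nail. Nobody is named as the reader. No section separates reading from treating, removes arm, visit or date from the image, or calls for a second reading. The staff named as handling the photographs and the responder table belong to the treating team.

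Open-label treatment does not require open-label reading, because the photographs are stored files. Unless masking is written in, a reader may know which image is the later one and which arm the subject is in. Section 3.2 puts a direction on record by suggesting that blue light would help.

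Two results are at stake. The first is the responder rate judged against 50%, where no concurrent untreated arm would carry the same error and offset it. The second is the comparison of red with red-and-blue light.

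**Working it through.** **Figure in the plan.** The plan gives no figure for reading error to reproduce. Section 3.3 calls 100 patients adequate ("a sample size of 100 patients is adequate to establish statistical significance of our results") without a power or formula. That statement concerns the historical cure rate and is not in dispute here.

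**Which errors matter.** Let the baseline reading be B + e0 and the later reading F + e1, where e0 and e1 are reading errors. The measured change is (F − B) + (e1 − e0).
- If e1 = e0, for example a border always placed 0.5 mm too far distally, the error cancels.
- If e1 − e0 = d > 0, every measured change rises by d.
- If d differs between arms, the difference in mean change between arms is biased by the difference in d.

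**Decision rule.** Inputs from the plan are n = 100 and a one-sided 95% lower bound of at least 50%. The exact (Clopper-Pearson) lower bound is 0.503 for 59/100 and 0.493 for 58/100, so 59 responders are needed. The Wilson and Wald bounds also first reach 50% at 59 (0.508 and 0.509). With unbiased reading, P(X ≥ 59 | n = 100, p = 0.50) = 4.4%.

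**Sensitivity to d.** The plan gives no SD of change and no reader variability, so these are assumptions: normally distributed change, true rate 50% (mean change at the 3 mm threshold), and SD 2 mm with a range of 1.5 to 3 mm. The apparent rate is Φ(d/SD), and the chance of meeting the rule is P(X ≥ 59 | 100, apparent rate).

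| d | Apparent rate, SD 2 mm | Chance of meeting the rule, SD 2 mm | Range over SD 3 to 1.5 mm |
|---|---|---|---|
| 0 | 50% | 4.4% | 4.4% |
| 0.25 mm | Φ(0.125) = 55% | 24% | 15–35% |
| 0.5 mm | Φ(0.25) = 60% | 61% | 35–83% |

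**With dropout.** Section 3.4 (Follow-up) counts dropouts as failures. With an assumed 10% dropout and SD 2 mm, the apparent rate is 0.9 × Φ(d/SD):
- d = 0: 0.9 × 0.500 = 0.450, chance 0.3%
- d = 0.25 mm: 0.9 × 0.550 = 0.495, chance 3.5%
- d = 0.5 mm: 0.9 × 0.599 = 0.539, chance 18%

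**Away from the boundary.** With no dropout and unbiased reading, the rule is met with probability 91% at a true rate of 65% and 99% at 70%. Reading error then changes the pass decision little, but it still inflates the reported rate. At a true 65% with SD 2 mm and d = 0.5 mm, the apparent rate is Φ(Φ⁻¹(0.65) + 0.25) = 74%.

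**The case against.** **Unmasked reading is inferred from silence.** A reader might take the open-label entry to mean that photographs will be read with arm and visit known. The documents do not say that. The entry describes the trial, no reader is named, and the photography protocol is still to be put in place. What stands is narrower: nothing in the plan prevents unmasked reading.

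**Safeguards exist.** The midline landmark rule, the ruler, standardised images and the software check all reduce measurement error. The plan does not limit the software to setting the scale, so it should not be dismissed as doing only that. Still, none of these is described as hiding arm or visit from the reader, and the software step is not explained.

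**A change score removes consistent error.** One might infer that any steady misreading goes into the success rate. It does not, as the algebra shows; only error that differs by visit or arm survives.

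**The photograph is not the whole endpoint.** Mycological cure is the second primary component and is less open to a photograph reader's expectation. Section 3.6 also reports clear nail with concurrent cure as a tier of its own, so an over-read nail must still be mycologically negative to count there. This stands, but section 3.4 uses the photograph reading to select the nails assessed for mycology.

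**The illustration sits at the boundary.** This is fair. Dropout and a higher true rate both weaken the effect on the pass decision, as the figures above show.

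**Masking may be imperfect.** Methylene blue staining and repeated debridement may show that an image is post-treatment. This limits masking to visit, which is what matters for the 50% bound. Both arms receive the photosensitizer, so staining alone need not reveal the arm.

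**Conclusion.** The concern holds as a gap in protection for the clear-nail component, and the change should be made. The plan rests a yes/no call at 3 mm, a 50% bound and the selection of nails for mycology on photograph readings, and does not hide arm or visit from the reader. The risk is confined to error that differs by visit or by arm.

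In size, an assumed differential over-reading of 0.25 to 0.5 mm at a true rate of 50% and SD 2 mm takes the false-pass chance from 4.4% to between 24% and 61% without dropout. With 10% dropout it goes from 0.3% to between 3.5% and 18%. At true rates of 65% or more the rule is usually met anyway, and the harm is an inflated estimate. The SD, shift and dropout values are assumptions, so these figures show sensitivity and do not predict a bias. The documents do not support saying that biased reading will occur or that the photographs alone settle the primary endpoint.

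**What to change.** Add to section 3.4, at least for the baseline image and the endpoint images (end of procedure administration and 6 months):

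- Before measurement, each photograph is copied with subject number, site, arm, visit and date removed and the ruler kept.
- Copies receive a random code and are read in random order.
- The existing measuring staff do the reading, where possible on subjects they did not treat, by swapping images between the three sites.
- All readings are locked before the code is broken.

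**Cost.** Protocol wording, file handling and a short delay before readings are available. Sample size, visits and procedures are unchanged, and no reader is added. Limiting the minimum to baseline and endpoint images keeps the load to at most 3 × 100 = 300 files, against about 12 × 100 = 1,200 if every pre-treatment photograph were coded. The swap between sites is worded as where possible because the plan does not identify the measuring staff.

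**Limit.** Staining or debridement may leave masking to visit incomplete, and the report should say so. Masking to arm remains achievable.

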## 3.1 Overview of Study

### Definition of distal subungual onychomycosis (DSO)

This type of onychomycosis is the most common clinical presentation, in which the distal nail plate is separated from the nail bed. This infection presents as nails with normal surface texture and thickness but variable “bays” of white nail that extend from the distal nail tip proximally into

the area of the nail bed. This form has been the cornerstone of antifungal drug studies. Since it generally does not involve the nail matrix, it is more amenable to improvement in clinical appearance than some other forms. In this trial only mild to moderate DSO cases will be included using the Onychomycosis Severity Index (OSI). An OSI score is obtained by multiplying the score for the area of involvement (range, 0-5) by the score for the proximity of disease to the matrix (range, 1-5).

A clinician or delegate will:

- Take representative before and after photos of nail/s prior to treatment.
- Provide a description of the treatment protocol used, including any adjunctive interventions such as topical antifungal products or debridement.
- Record occurrences and frequency of any adverse events.
- Prepare a table summarizing the percent complete responders, partial responders (which may be further stratified), and non-responders.
- Ensure that fungal species are assessed.
- Ensure that clinical presentations of onychomycosis are assessed (e.g., DSO).

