#### Inclusion Criteria

We are seeking otherwise healthy males or females who meet the following criteria:

- are between 18-75 years of age.
- have a clinical diagnosis of mild to moderate DSO in the nail of at least one great toe, with 20% to 50% clinical involvement of the target toenail, without dermatophytomas or lunula (matrix) involvement, without lunular or proximal involvement.
- exhibit positive mycology results (i.e., KOH test and culture of a dermatophyte) from the target great toenail, confirming common dermatophytes such as *T. rubrum*.

- are willing to refrain from using polish or other medication on treated toenails or on the skin immediately adjacent to the toenails during the treatment period unless directed to do so by the investigator.
- are willing to refrain from using topical steroids or topical antifungals on toenails or the skin immediately adjacent to the toenails or systemic antifungals for the duration of the study.
- are willing to provide signed and dated written voluntary informed consent in English before any protocol-specific procedures are performed.
- are able to complete the study and comply with study instructions.

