## **4.4 Subject Withdrawal**

Subjects may be withdrawn from the study for any of the following reasons:

1. Subject's choice to withdraw their consent to participate. Any participant has the right to withdraw from the study at any time and for any reasons without prejudice to future medical care by the physician or the institution.
2. Investigator's choice to withdraw the subject from the study. An investigator may choose to withdraw a subject from the study due to changes to their medical condition which could interfere with their participation or if the study may interfere with their prompt and effective treatment.
3. Study termination for either administrative or safety reasons.

For participants who withdraw their consent for study participation, the Investigator will complete the "Subject Withdrawal" and no additional data will be collected after the date of their discontinuation.

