## **6.3 Protocol Deviations**

A protocol deviation is defined as any study action taken by the clinical Investigator or site personnel in conflict with the Study Protocol. Investigators must make every effort to follow the protocol except where necessary to protect the life or physical well being of a subject in an emergency. All deviations from the protocol will be reported on the appropriate Deviations Log.

Deviations must be reported to the Sponsor within a reasonable time frame. Subject specific deviations will be reported on the Deviations Log. Non-subject specific deviations, (e.g. unauthorized use of an investigational device outside the study, etc.), will be reported to the Principal Investigator.

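### Section 3.4 counts a subject who uses a barred antifungal and gains 3 mm of clear nail as a responder toward the 50% bound (minor)

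*Combined protocol and SAP*

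**What the plan says.** Section 3.4 defines response for a nail by growth alone: "Individual toenail success criterion is defined as 3 millimeter (mm) or more of clear nail growth as evaluated relative to baseline". The study-level target is in the same section: "The 95% one-sided confidence interval (i.e., lower bound only) around the observed response rate as described below should be" at least 50%. The follow-up paragraph of 3.4 adds the only rule that overrides the nail result: "subjects who drop out or are lost to follow-up will be considered as treatment failures".

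The bar on other treatment appears as a commitment at entry. Section 1.0 requires that subjects "are willing to abstain from any other treatment for onychomycosis for the duration of the pilot study". The inclusion criteria in 3.5 require, throughout the study, that they "are willing to refrain from using topical steroids or topical antifungals on toenails or the skin immediately adjacent to the toenails or systemic antifungals". Neither place gives a consequence for use after entry.

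Four other places bear on the point:
- **3.1** has the clinician describe the treatment given, "including any adjunctive interventions such as topical antifungal products or debridement".
- **4.4** lets the investigator withdraw a subject "due to changes to their medical condition which could interfere with their participation", or where staying in the study could get in the way of timely, effective care.
- **6.3** states: "A protocol deviation is defined as any study action taken by the clinical Investigator or site personnel in conflict with the Study Protocol". It also sends subject-specific deviations to the Deviations Log.
- **1.0, 3.4 and 3.6** add mycology: cure by culture is part (b) of the primary endpoint, negative mycology is assessed among clear-nail responders, and results are reported in tiers.

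**The concern.** The study is meant to establish the efficacy of this device. Both arms receive it, and the response rate is judged against a fixed 50% bound, so no untreated arm would show clearing caused by another drug. If a subject clears on a barred antifungal, that drug's effect is credited to the device, and the error runs only upward.

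The plan also treats similar subjects differently. It fails drop-outs so that losing subjects with poor visual results does not flatter the rate. Those subjects have the most reason to seek another antifungal. One who leaves is a failure, while one who stays, takes an oral antifungal and clears is a responder. Because the study is open label and the plan is silent, the handling of users could also be settled after results are known.

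**Working it through.** **Step 1: does any section change the score?**
- 3.4, clear nail: growth of 3 mm or more, with no condition on other treatment.
- 3.4, follow-up: fails drop-outs and losses only.
- 3.4 mycology and 3.6 tiers: no condition on antifungal use. A nail cleared by an oral antifungal could meet both.
- 4.4: withdrawal is at the investigator's discretion, and antifungal use is not named as a ground.
- 3.1 and 6.3: use can be recorded, but recording alters no score.

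So a user who stays in and gains 3 mm is a clear-nail responder.

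**Step 2: the pass threshold.** The plan calls 100 subjects adequate but gives no power or formula, so there is no derived figure to reproduce. The 50% rule can be worked out directly. With n=100, both arms pooled (an assumption, since 3.4 does not say whether the bound is pooled or per arm), the one-sided 95% lower bounds are:

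| Responders | Exact | Wilson | Wald |
|---|---|---|---|
| 58 | 0.493 | 0.498 | 0.499 |
| 59 | 0.503 | 0.508 | 0.509 |

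The study passes at 59 or more under all three methods. Pass chance = P(X ≥ 59 | n=100, p). At p=0.50 this is 0.0443. One reclassified subject can decide the result: 59 responders including one user becomes 58, which fails.

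**Step 3: size of the upward error.** Assumed inputs: 2 or 5 users per 100 (the documents give no figure) and a true device-alone rate of 50%. The cure rates in 2.0 (topical 6-23% at one year, oral 45-70%) stand in for the chance that the antifungal alone yields 3 mm.

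(A) Users would all otherwise fail: p = 0.50 + (users/100) × cure rate.
(B) Use is unrelated to response: p = 0.50 + (users/100) × 0.5 × cure rate.

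Example, (A), 5 oral users at 70%: p = 0.50 + 0.05 × 0.70 = 0.535, pass chance 0.1581.

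| Users, cure rate | (A) | (B) |
|---|---|---|
| 2, topical 6% | 0.0466 | 0.0454 |
| 2, topical 23% | 0.0536 | 0.0488 |
| 5, topical 6% | 0.0502 | 0.0472 |
| 5, topical 23% | 0.0704 | 0.0562 |
| 2, oral 45% | 0.0639 | 0.0534 |
| 2, oral 70% | 0.0774 | 0.0591 |
| 5, oral 45% | 0.1052 | 0.0697 |
| 5, oral 70% | 0.1581 | 0.0881 |

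**Step 4: cost of scoring users as non-responders.** Under (A) nothing is lost, because users would have failed anyway. Under (B), p = true rate × (1 − share of users):

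| True rate | No users | 2% users | 5% users |
|---|---|---|---|
| 0.50 | 0.044 | 0.029 | 0.014 |
| 0.60 | 0.623 | 0.527 | 0.383 |
| 0.65 | 0.912 | 0.860 | 0.750 |
| 0.70 | 0.993 | 0.984 | 0.953 |

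At a true 60% the loss is 9.6 points (2 users) or 24.0 points (5 users); at 65% it is 5.2 or 16.3 points. The bias removed under (B) is at most 5.91 − 4.43 = 1.5 points (2 users) or 8.81 − 4.43 = 4.4 points (5 users), both for oral use at 70%.

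**The case against.** The strongest case against this point concerns its size and remedy, since 3.4 plainly states no rule for antifungal use.

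**Capture.** A reader might infer from the definition in 6.3 that a subject's own antifungal use would go unrecorded. The documents do not support that: the same section logs subject-specific deviations, and 3.1 asks for adjunctive topical antifungals to be described. The gap is in scoring.

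**Withdrawal.** A subject doing badly who needs an oral antifungal could fit the second ground in 4.4, be withdrawn, and count as a failure if treated as a drop-out. That route exists but is discretionary and not tied to antifungal use, so it narrows the gap without closing it.

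**Mycology.** A reader might infer that such a subject is a full device success whatever the mycology shows. That goes too far. The 3 mm rule is the clear-nail criterion only; mycological cure is part (b) of the primary endpoint, and 3.6 reports tiers. Neither is conditional on antifungal use, so the gap remains within each.

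**Magnitude.** Cure rates are not 3 mm rates, and a subject who starts an antifungal late has less time to grow clear nail. The 15.8% needs five oral users, all otherwise failures, each with the full 70% effect. This stands, and it limits the claim.

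**Remedy.** If use is unrelated to response, the non-responder rule overcorrects and costs more pass probability at a true 60-65% than the bias it removes, for oral as well as topical use. Making the as-observed result primary would also be defensible. This stands too, and is why both results must be shown.

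**Conclusion.** The point holds as a minor one. As written, a subject who remains in the study, uses a barred antifungal and gains 3 mm counts toward the 50% bound, and no other section changes that score.

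A reader might infer that the primary result is seriously at risk. The documents do not support this: the entry commitments and the exclusion of recent antifungal users make frequent use unlikely, and topical use moves the false-pass chance by at most 2.6 points (7.0% against 4.4%). The larger figures apply to oral use among subjects who would otherwise fail.

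All figures rest on an assumed 2 to 5 users per 100, a pooled n=100, and the cure rates in 2.0 standing in for the 3 mm endpoint, with the net direction of that last error unknown.

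**What to change.** Add to 3.4: 'A subject who uses a systemic antifungal, or a topical antifungal on the target nail or adjacent skin, between first treatment and the clear-nail assessment used for the 50% bound counts as a non-responder, as drop-outs do. The as-observed response rate and its lower bound will be reported beside this result.' Record topical and systemic antifungal use with start and stop dates, building on the existing duty in 3.1. Do this before results are seen.

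The direct cost is two sentences and one dated data field, with no added visits or subjects. The statistical cost is a lower headline rate. If use is unrelated to response, the rule is conservative, with a false-pass chance of 2.9% (2 users) or 1.4% (5 users), and the pass chance drops as tabulated above. For example, at a true 60% it falls from 0.62 to 0.53 or 0.38. Showing both results lets the reader see whether the conclusion depends on how users are scored.
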